Deep venous thrombosis, pulmonary embolism, myocardial infarction, and stroke occur in subjects with multiple myeloma treated with pomalidomide. Antithrombotic prophylaxis is recommended for subjects with a history of cardiovascular disease or per investigator discretion. Refer to the pomalidomide package insert for details.¹⁰

Management of Infection

Subjects should receive anti-infective prophylaxis (e.g., amoxicillin/clavulanic acid or levofloxacin or equivalent per institutional guidelines) at least during the first 90 days of study and upon disease

progression for at least 30 days unless contraindicated per investigator discretion. Furthermore, subjects deemed at high risk of infection should receive immunoglobulin replacement therapy (i.e., IVIG) per institutional guidelines or at the investigator's discretion.

The use of antibiotics that are moderate or strong CYP3A inhibitors should be avoided or used with caution and with appropriate venetoclax dose modification (refer to [Appendix I](#)) as per protocol.

All subjects receiving venetoclax should be closely monitored for infections and in the event of a Grade ≥ 3 or serious infection, treatment with venetoclax should be interrupted and upon resolution, treatment can be either resumed at a reduced dose or discontinued, depending on investigator's clinical judgment.

Please refer to [Table 9](#) and [Table 10](#) for guidance on dose interruptions and/or reductions related to venetoclax toxicities.

Potential for drug-drug interactions should be considered. Please refer to [Appendix J](#) for a description of prohibited and cautionary medications.

Management of Other Toxicities

If other events occur that are related to venetoclax or pomalidomide, the investigator may interrupt or dose reduce venetoclax and/or pomalidomide, as appropriate (refer to [Appendix I](#)).

Pomalidomide must be permanently discontinued for angioedema, skin exfoliation, bullae, or any other severe dermatologic reaction.

All subjects should be monitored for new onset hematologic, hepatic, and renal toxicities with dose delay or reduction as appropriate. Please follow local, approved product label or applicable summary of product characteristics¹² for monitoring guidelines for pomalidomide or [Appendix I](#) for venetoclax.

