6.5 Dose-Limiting Toxicity

DLTs for dose-escalation purposes will be determined during the first cycle (28 days) of study drug administration at the designated cohort dose. AEs occurring following Cycle 1 will also be evaluated by the investigator and the AbbVie TA MD and may be considered as dose limiting. Any of the following events that concur with the administration of venetoclax, pomalidomide, or dexamethasone, which cannot be attributed by the investigator to a clearly identifiable cause such as disease progression, concurrent illness, or concomitant medication, will be considered a DLT:

- Grade 4 neutropenia lasting more than 7 days
- Grade 3 or Grade 4 neutropenia with fever
- Grade 4 thrombocytopenia that has not recovered before the start of the next cycle of therapy

- Grade 2 or higher bleeding associated with Grade ≥ 3 thrombocytopenia
- Unexpected Grade 2 or higher toxicity which requires dose modification or delay of ≥ 1 week
- Clinical TLS
- Laboratory TLS if the metabolic abnormalities are deemed clinically significant by the investigator
- All other Grades 3, 4, or 5 AEs with the exception of the following:
 - Grades 3, 4 afebrile neutropenia
 - Grade 3 thrombocytopenia that does not result in bleeding
 - Grades 3, 4 lymphopenia
 - Grades 3, 4 leukopenia
 - Grade 3 or 4 hyperuricemia or hypocalcemia or Grade 3 hyperkalemia, if transient (i.e., lasting < 48 hours) and without manifestations of clinical TLS (i.e., creatinine $\geq 1.5 \times$ ULN, cardiac arrhythmias, sudden death, or seizures)
 - Grade 3 fatigue
 - Grade 3 peripheral neuropathy
 - Grade 3 nausea, vomiting, and/or diarrhea that are responsive to treatment
 - Grade 3 hyperglycemia that is controllable with insulin or oral hyperglycemic agents within 24 hours
 - Grade 3 hypertension that is reversible within 24 hours
 - Grade 3 confusion that is reversible within 24 hours
 - Grade 3 or higher local reaction to subcutaneous injections that does not resolve within 24 hours
 - Grade 3 insomnia that is managed with a sedative or reversible within 24 hours
 - Grade 3 edema that is controlled with diuretics or reversible within 24 hours
 - Grade 3 dyspepsia that is managed with histamine 2 blockers/proton pump inhibitors or reversible within 24 hours

Any DLTs observed during the designated cohort dosing period will require a modification of the designated cohort dose as directed per the dose-escalation guidelines (Section 4.1).

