Any DLT will require an interruption and possible discontinuation of venetoclax, pomalidomide, and/or dexamethasone. Venetoclax, pomalidomide, and/or dexamethasone may be reintroduced at a reduced dose if the toxicity grade returns to \leq Grade 1 or to baseline if Grade 2 at study entry.

Drug interruption for up to 72 hours following transient (i.e., lasting < 48 hours) chemical changes and laboratory TLS may be allowed and may not be considered a DLT or require a dose reduction. If the TLS

has not resolved within 72 hours, then a dose reduction should be considered. The subject may be allowed to re-escalate to the final dose based on a risk assessment (including tumor burden status).

Any reduced dose level of venetoclax, pomalidomide, and/or dexamethasone will be defined by AbbVie after discussion between the investigator and the AbbVie TA MD. The dose of venetoclax, pomalidomide, and/or dexamethasone may be increased thereafter as defined by AbbVie after discussion between the investigator and the AbbVie TA MD. The venetoclax dose is not to exceed the highest tolerated dose level. All decisions regarding continued dosing for individual subjects will be medically managed by the investigator, in conjunction with the AbbVie TA MD, as appropriate. These decisions will be driven by the definition of DLTs as described above.

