Blood chemistry changes or symptoms suggestive of TLS	
 • Withhold the next day's dose. If resolved within 24 – 48 hours of last dose, resume at the same dose. • For any blood chemistry changes requiring more than 48 hours to resolve, resume at a reduced dose. • For any events of clinical TLS, resume at a reduced dose following resolution.

ANC = absolute neutrophil count; G-CSF = granulocyte-colony stimulating factor; TLS = tumor lysis syndrome

Table 11. Toxicities Related to Pomalidomide

Toxicity	Recommended Action
Neutropenia: ANC $< 0.5 \times 10^9/L$, or febrile neutropenia (fever $\geq 38.5^\circ C$ and ANC $< 1 \times 10^9/L$)	
 • Interrupt pomalidomide treatment, follow complete blood counts weekly. Add G-CSF (at discretion of the treating physician). • ANC returns to $\geq 0.5 \times 10^9/L$ (or per local guidelines), resume pomalidomide treatment at 3 mg/day. • For each subsequent drop to $< 0.5 \times 10^9/L$, interrupt pomalidomide treatment. • ANC returns to $\geq 1 \times 10^9/L$, resume pomalidomide treatment at 1 mg less than the previous dose.^a
Thrombocytopenia: Platelet count $< 25 \times 10^9/L$	
 • Interrupt pomalidomide treatment for remainder of cycle. • Platelet count returns to $\geq 50 \times 10^9/L$, resume pomalidomide treatment at 1 dose level lower.
Angioedema: Grade 4 rash, exfoliative or bullous rash	
 • Permanently discontinue pomalidomide.
Other Grade 3/4 toxicities judged to be related to pomalidomide	
 • Interrupt pomalidomide treatment. • Restart treatment at 1 dose level lower than the previous dose when toxicity has resolved to \leq Grade 2 at the physician's discretion.

ANC = absolute neutrophil count; G-CSF = granulocyte-colony stimulating factor

a. If adverse reactions occur after dose reductions to 1 mg, then study drug should be discontinued.

Table 12. Toxicities Related to Dexamethasone

Toxicity	Recommended Action
Dyspepsia = Grades 1 – 2	Maintain dose and treat with histamine (H2) blockers or equivalent. Decrease by 1 dose level if symptoms persist.
Dyspepsia ≥ Grade 3	Interrupt dose until symptoms are controlled. Add H2 blocker or equivalent and decrease 1 dose level when dose restarted.
Edema ≥ Grade 3	Use diuretics as needed and decrease dose by 1 dose level.

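### Table 11's permanent-stop row for pomalidomide omits Section 6.4's catch-all for other severe skin reactions, so some of these meet a row that permits, at the physician's discretion, a restart at a lower dose

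*Protocol*

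**What the plan says.** Two places in the protocol govern pomalidomide after a serious skin reaction.

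**Section 6.4, Management of Other Toxicities.** The paragraph opens with a general permission: "If other events occur that are related to venetoclax or pomalidomide, the investigator may interrupt or dose reduce venetoclax and/or pomalidomide, as appropriate". It points to Appendix I for details. A separate sentence then sets a mandatory rule: "Pomalidomide must be permanently discontinued for angioedema, skin exfoliation, bullae, or any other severe dermatologic reaction".

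**Appendix I, Table 11 (toxicities related to pomalidomide).** The row whose action is permanent discontinuation is labelled "Angioedema: Grade 4 rash, exfoliative or bullous rash". The last row is labelled "Other Grade 3/4 toxicities judged to be related to pomalidomide". Its action is to interrupt and then: "Restart treatment at 1 dose level lower than the previous dose when toxicity has resolved to" Grade 2 or lower, at the physician's discretion. Skin events are not excluded from this last row. The column is headed as recommended action.

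Section 6.4 also says, near its start, that dose modifications for toxicities of each study drug are found in Appendix I. Neither document says which text prevails if the body and the appendix differ. The SAP does not deal with dose modification.

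**The concern.** The table is what a site is likely to have open when deciding on a dose, and Section 6.4 sends the reader there. If the table carries only part of a mandatory stopping rule, an investigator working from it could treat a severe skin reaction as an ordinary Grade 3 or 4 toxicity. The subject could then be re-exposed to pomalidomide after an event for which the body of the protocol requires a permanent stop. What is at stake is the safety of an individual subject and consistent handling across sites. The trial's statistical properties are not involved.

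**Working it through.** No figure is involved, so the check is a comparison of the texts.

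**Step 1: compare the two lists.** I treat skin exfoliation and bullae in Section 6.4 as the same events as exfoliative and bullous rash in Table 11. The remaining pomalidomide-related skin reactions are split by rash or non-rash and by Grade 3 or 4.

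| Reaction | Section 6.4 | Table 11 |
|---|---|---|
| Angioedema | Permanent stop | Permanent stop |
| Exfoliative or bullous | Permanent stop | Permanent stop |
| Other rash, Grade 4 | Permanent stop (catch-all) | Permanent stop (named) |
| Other non-rash reaction, Grade 4 | Permanent stop (catch-all) | Last row: restart permitted |
| Other rash, Grade 3 | Permanent stop if judged severe | Last row: restart permitted |
| Other non-rash reaction, Grade 3 | Permanent stop if judged severe | Last row: restart permitted |

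The first three lines agree. The fourth is a firm difference. The last two depend on what severe means.

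**Step 2: what severe means.** Section 6.4 gives no grade. The only severity words tied to grades are in Section 6.1, in the fallback scale for adverse events that CTCAE does not capture. It describes Grade 4 as severe and Grade 3 as moderate to severe. That scale does not formally apply to events that CTCAE grades, but it shows that Grade 4 is severe on the protocol's own usage and that Grade 3 is arguable. If severe means Grade 4 only, the gap is the fourth line alone. If it reaches into Grade 3, the last two lines join it.

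**Step 3: does Section 6.5 close the gap?** In Cycle 1, the dose-limiting toxicity (DLT) definition includes "All other Grades 3, 4, or 5 AEs with the exception of the following", and skin reactions to the oral study drugs are not among the exceptions. A Grade 3 or 4 skin reaction with no other clear cause is therefore a DLT. The section then says: "Venetoclax, pomalidomide, and/or dexamethasone may be reintroduced at a reduced dose if the toxicity grade returns to" Grade 1 or lower, or to baseline if that was Grade 2. This recovery threshold is stricter than the one in Table 11, but reintroduction is still allowed and no exception is made for skin reactions. For later cycles: "AEs occurring following Cycle 1 will also be evaluated by the investigator and the AbbVie TA MD and may be considered as dose limiting". That adds a review without adding a stopping rule.

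**Step 4: oversight.** Section 6.5 also has the sponsor define any reduced dose level after the investigator and the sponsor's medical director have discussed it. Decisions on continued dosing are managed by the investigator together with the medical director, as appropriate. A second person is therefore likely to see the case, but neither sentence restores the missing words.

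**The case against.** The best defence is that both texts can be followed at once. Section 6.4 says must. Appendix I is titled as recommended dose reductions, its column is headed as recommended action, and the restart is left to the physician's discretion. An investigator who declines to restart complies with both, and discretionary guidance does not displace a mandatory rule. In Section 6.4 the mandatory sentence comes straight after a pointer to Appendix I, so a reader who starts there meets the stop first. Table 11 already covers Grade 4 rash, which can be read as the catch-all put into graded terms. The sponsor also takes part in setting reduced doses.

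Most of this stands. Section 6.4 is the better reading, and these points are why the matter is minor. They do not remove it. No precedence rule is written down, the permissive row does not exclude skin events, and the table leaves Grade 4 non-rash reactions uncovered.

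A reader might infer more: that the protocol directs sites to rechallenge after severe skin reactions, or that every such reaction falls into the restart row. The documents support neither. The restart is permitted and not required, it applies only to events judged related to pomalidomide, and angioedema, exfoliative or bullous rash and Grade 4 rash are permanent stops in both places. Nor do the documents support describing this as an unsupervised route back to treatment.

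**Conclusion.** The inconsistency is real and minor. Table 11 omits part of a mandatory stopping rule, and its last row gives a permissive instruction for the events left out. The firm conflict is one category, a pomalidomide-related Grade 4 skin reaction that is not a rash, angioedema, exfoliative or bullous. Grade 3 reactions outside the named types conflict only if judged severe.

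The conclusion rests on three points: both texts are in force, no precedence rule exists, and the last row is read as written, with skin events inside it. The documents give no frequency for these reactions, so no count of affected subjects is offered. Sample size, alpha, power and the planned analyses are unaffected.

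**What to change.** - In Table 11, extend the permanent-stop row with 'or other severe dermatologic reactions (see Section 6.4)'.
- In the last row of Table 11, for other Grade 3 or 4 toxicities, add 'excluding the dermatologic reactions above'.
- Preferably, state in Section 6.4 which grade counts as severe for a skin reaction. Without this, Grade 3 events remain a matter of judgement even after the two tables' texts agree.

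The cost is a few words in two table rows and one clarification in Section 6.4, which can go into the next amendment. Data collection and analysis do not change.

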6.5 Dose-Limiting Toxicity

DLTs for dose-escalation purposes will be determined during the first cycle (28 days) of study drug administration at the designated cohort dose. AEs occurring following Cycle 1 will also be evaluated by the investigator and the AbbVie TA MD and may be considered as dose limiting. Any of the following events that concur with the administration of venetoclax, pomalidomide, or dexamethasone, which cannot be attributed by the investigator to a clearly identifiable cause such as disease progression, concurrent illness, or concomitant medication, will be considered a DLT:

- Grade 4 neutropenia lasting more than 7 days
- Grade 3 or Grade 4 neutropenia with fever
- Grade 4 thrombocytopenia that has not recovered before the start of the next cycle of therapy

- Grade 2 or higher bleeding associated with Grade ≥ 3 thrombocytopenia
- Unexpected Grade 2 or higher toxicity which requires dose modification or delay of ≥ 1 week
- Clinical TLS
- Laboratory TLS if the metabolic abnormalities are deemed clinically significant by the investigator
- All other Grades 3, 4, or 5 AEs with the exception of the following:
 - Grades 3, 4 afebrile neutropenia
 - Grade 3 thrombocytopenia that does not result in bleeding
 - Grades 3, 4 lymphopenia
 - Grades 3, 4 leukopenia
 - Grade 3 or 4 hyperuricemia or hypocalcemia or Grade 3 hyperkalemia, if transient (i.e., lasting < 48 hours) and without manifestations of clinical TLS (i.e., creatinine $\geq 1.5 \times$ ULN, cardiac arrhythmias, sudden death, or seizures)
 - Grade 3 fatigue
 - Grade 3 peripheral neuropathy
 - Grade 3 nausea, vomiting, and/or diarrhea that are responsive to treatment
 - Grade 3 hyperglycemia that is controllable with insulin or oral hyperglycemic agents within 24 hours
 - Grade 3 hypertension that is reversible within 24 hours
 - Grade 3 confusion that is reversible within 24 hours
 - Grade 3 or higher local reaction to subcutaneous injections that does not resolve within 24 hours
 - Grade 3 insomnia that is managed with a sedative or reversible within 24 hours
 - Grade 3 edema that is controlled with diuretics or reversible within 24 hours
 - Grade 3 dyspepsia that is managed with histamine 2 blockers/proton pump inhibitors or reversible within 24 hours

Any DLTs observed during the designated cohort dosing period will require a modification of the designated cohort dose as directed per the dose-escalation guidelines (Section 4.1).

Any DLT will require an interruption and possible discontinuation of venetoclax, pomalidomide, and/or dexamethasone. Venetoclax, pomalidomide, and/or dexamethasone may be reintroduced at a reduced dose if the toxicity grade returns to \leq Grade 1 or to baseline if Grade 2 at study entry.

Drug interruption for up to 72 hours following transient (i.e., lasting < 48 hours) chemical changes and laboratory TLS may be allowed and may not be considered a DLT or require a dose reduction. If the TLS

has not resolved within 72 hours, then a dose reduction should be considered. The subject may be allowed to re-escalate to the final dose based on a risk assessment (including tumor burden status).

Any reduced dose level of venetoclax, pomalidomide, and/or dexamethasone will be defined by AbbVie after discussion between the investigator and the AbbVie TA MD. The dose of venetoclax, pomalidomide, and/or dexamethasone may be increased thereafter as defined by AbbVie after discussion between the investigator and the AbbVie TA MD. The venetoclax dose is not to exceed the highest tolerated dose level. All decisions regarding continued dosing for individual subjects will be medically managed by the investigator, in conjunction with the AbbVie TA MD, as appropriate. These decisions will be driven by the definition of DLTs as described above.

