- platelets $\geq 50,000/\text{mm}^3$
- all other AEs should resolve to \leq Grade 2

Subjects will receive venetoclax and pomalidomide until documented disease progression, documented unacceptable toxicity, withdrawal of consent, or the subject meets other criteria for discontinuation per study protocol (Section 5.5). Subjects will remain on study treatment as long as venetoclax or pomalidomide/dexamethasone is being administered. Subjects may discontinue pomalidomide/dexamethasone but may continue receiving venetoclax QD as monotherapy for up to 2 years following the date of the last subject enrolled on study provided the subject completed venetoclax plus pomalidomide and dexamethasone dosing in Cycle 1, continue to tolerate venetoclax, have no evidence of disease progression, and do not meet any criteria for treatment discontinuation. For subjects that

continue to derive benefit after 2 years of treatment following the date of the last subject enrolled, AbbVie will work with the investigator to evaluate options for continuation of venetoclax therapy.

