The AbbVie Therapeutic Area Medical Director (TA MD) identified in [Appendix L](#) should be contacted if there are any questions regarding concomitant or prior therapy(ies) and venetoclax or pomalidomide dose reductions.

Table 9. Study Drug Dose Levels

Dose	Venetoclax	Pomalidomide	Dexamethasone (< 75 years of age)	Dexamethasone (≥ 75 years of age)
Starting dose	800 mg	4 mg	40 mg	20 mg
Dose level –1	600 mg	3 mg	20 mg	12 mg
Dose level –2	400 mg	2 mg	12 mg	8 mg
Dose level –3	200 mg	1 mg	8 mg	4 mg

Table 10. Toxicities Related to Venetoclax

Toxicities	Recommended Action
Grade 3 or Grade 4 neutropenia with infection or fever; or Grade 4 hematologic toxicities (except for lymphopenia)	
 • G-CSF or growth factors for neutropenia should be administered with venetoclax if clinically indicated. • For Grade 4 neutropenia (ANC < 500 cells/μL) without infection, anti-infective prophylaxis (e.g., amoxicillin/clavulanic acid or levofloxacin or equivalent per institutional guidelines) is recommended until the neutropenia improves to Grade 3 or better (ANC > 500 cells/μL). • First episode: Interrupt venetoclax and once the toxicity has resolved to Grade 1 or baseline level, venetoclax may be resumed at the same dose. • For subsequent episodes: Interrupt venetoclax. Consider using G-CSF as clinically indicated. Follow dose reduction guidelines when resuming treatment with venetoclax after resolution. A larger dose reduction may occur at the discretion of the investigator and according to the dose reduction guidelines.
Grade \geq 3 or serious infections	
 • Interrupt venetoclax and upon resolution, treatment can either be resumed at a reduced dose (see Table 9) or discontinued, at the discretion of the investigator.
Grade 3 or 4 non-hematologic events	
 • First episode: Interrupt venetoclax. Once toxicity has resolved to Grade \leq 1 or baseline, venetoclax may be resumed at the same dose. No dose modification is required. • For subsequent episodes: Interrupt venetoclax. Follow dose reduction guidelines when resuming treatment with venetoclax after resolution. A larger dose reduction may occur at the discretion of the investigator and according to the dose reduction guidelines.

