Confusion or mood alteration ≥ Grade 2	Interrupt dose until symptoms resolve. When dose restarted, decrease dose by 1 dose level.
Muscle weakness ≥ Grade 2	Interrupt dose until muscle weakness ≤ Grade 1. Restart with dose decreased by 1 level.
Hyperglycemia ≥ Grade 3	Decrease dose by 1 dose level. Treat with insulin or oral hypoglycemic agents as needed.
Acute pancreatitis	Discontinue dexamethasone treatment regimen.
Other ≥ Grade 3 dexamethasone-related adverse events	Stop dexamethasone dosing until adverse event resolves to ≤ Grade 2. Resume with dose reduced by 1 dose level.

APPENDIX J. SAMPLE LIST OF PROHIBITED AND CAUTIONARY MEDICATIONS THAT MAY INTERACT WITH STUDY DRUGS

Prohibited During Part 1, Cycle 1 and Cautionary in Part 1, ≥ Cycle 2 and in Part 2, All Cycles

Strong CYP1A2 inhibitors^{††} – ciprofloxacin, enoxacin, fluvoxamine, zafirlukast
 
Strong CYP3A inhibitors[†] – boceprevir, clarithromycin, cobicistat, conivaptan, danoprevir/ritonavir, elvitegravir/ritonavir, idelalisib,* indinavir, itraconazole, ketoconazole, lopinavir/ritonavir, mibefradil, nefazodone, nelfinavir, paritaprevir/ritonavir combinations, posaconazole, ritonavir, saquinavir, telaprevir, telithromycin, tipranavir/ritonavir, troleandomycin, voriconazole
 
Moderate CYP3A inhibitors[‡] – amprenavir, aprepitant, atazanavir, cimetidine, ciprofloxacin, clotrimazole, crizotinib,* cyclosporine,* darunavir/ritonavir, diltiazem,^a erythromycin, fluconazole, fosamprenavir, imatinib,* isavuconazole, tofisopam, verapamil
 
Strong CYP3A inducers – avasimibe, carbamazepine, enzalutamine, mitotane, phenytoin, rifampin, St John's wort
 
Moderate CYP3A inducers – bosentan, efavirenz, etravirine, modafinil, nafcillin

Cautionary

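### After a dose-limiting toxicity (DLT), Protocol Section 6.5 and Appendix I Tables 10 to 12 give different re-treatment rules for the same events (dose for venetoclax, recovery level for pomalidomide and dexamethasone), and no text says which prevails

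*Protocol*

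**What the plan says.** **Section 6.5** applies to every DLT: "Any DLT will require an interruption and possible discontinuation of venetoclax, pomalidomide, and/or dexamethasone". The drugs then "may be reintroduced at a reduced dose if the toxicity grade returns to" a stated level, namely at or below "Grade 1 or to baseline if Grade 2 at study entry". The only dose it names for re-treatment is a reduced one, with no exception for a first episode. It lists "Grade 3 or Grade 4 neutropenia with fever" as a DLT, and all other Grade 3 to 5 events outside a list of exceptions.

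**Section 6.4** sends sites to Appendix I for dose modification after drug-related toxicity and does not exempt DLTs.

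**Appendix I, Table 10 (venetoclax).** The row covering Grade 3/4 neutropenia with infection or fever allows the same dose after a first episode, once the toxicity is at Grade 1 or baseline. For a first Grade 3/4 non-hematologic event, "venetoclax may be resumed at the same dose. No dose modification is required".

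**Appendix I, Table 11 (pomalidomide).** For other related Grade 3/4 toxicities: "Restart treatment at 1 dose level lower than the previous dose when toxicity has resolved to" Grade 2 or lower, at the physician's discretion. For neutropenia, including febrile neutropenia, pomalidomide resumes at 3 mg/day when the ANC is back to at least 0.5 × 10⁹/L (or per local guidelines).

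**Appendix I, Table 12 (dexamethasone).** For other related events of Grade 3 or higher: "Stop dexamethasone dosing until adverse event resolves to" Grade 2 or lower, then resume one level down.

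**The concern.** Febrile neutropenia and non-excepted Grade 3/4 non-hematologic events are DLTs under Section 6.5 and also fall in rows of Appendix I. An investigator who opens Section 6.5 and one who opens Appendix I can therefore both follow the protocol and still re-treat the same event differently.

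Safety and tolerability is the primary objective. The subjects concerned are mainly those in Part 1, whose experience settles the expansion dose. Sections 6.1 and 6.5 bring toxicity after Cycle 1 into dose decisions, and SAP Section 7.1 summarizes adverse events by dose. The dose and recovery level at restart thus affect the individual subject's risk and the later-cycle data that the dose review considers.

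**Working it through.** There is no planned figure to reproduce, because the point rests on comparing texts. For events that Section 6.5 makes DLTs, the rules are:

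| First episode of | Section 6.5 (all drugs) | Table 10, venetoclax | Table 11, pomalidomide | Table 12, dexamethasone |
|---|---|---|---|---|
| Grade 3/4 neutropenia with fever | Reduced dose; Grade ≤ 1, or baseline if Grade 2 at entry | **Same dose**; Grade 1 or baseline | 3 mg/day; **ANC ≥ 0.5 × 10⁹/L** | No row of its own |
| Grade 3/4 non-hematologic event, not excepted | As above | **Same dose**; Grade ≤ 1 or baseline | Row for other toxicities: one level lower; **Grade ≤ 2** | Row for other events: one level lower; **Grade ≤ 2** |
| Grade ≥ 3 infection | As above | Reduced dose or discontinuation | – | – |
| Clinical tumor lysis syndrome | As above | Reduced dose | – | – |

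Bold entries differ from Section 6.5. Reading across:

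1. **Venetoclax.** The recovery level in Table 10 largely matches Section 6.5; the dose does not. The same-dose rule is for first episodes only, but a Cycle 1 DLT would ordinarily be a first episode. The infection and clinical tumor lysis rows do not use it.

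2. **Pomalidomide, other toxicities.** The dose direction agrees. The recovery level differs by one grade: 2 − 1 = 1.

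3. **Pomalidomide, neutropenia.** The starting dose is 4 mg, so 3 mg/day is a reduction and the dose direction agrees. For the recovery level, 0.5 × 10⁹ cells/L ÷ 10⁶ µL/L = 500 cells/µL. Section 6.4 and Table 10 describe an ANC above 500 cells/µL as Grade 3 or better. Restart just above that value is in the Grade 3 range, up to two grades short of the Section 6.5 level: 3 − 1 = 2.

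4. **Dexamethasone.** The dose direction agrees, and the row for other events differs from Section 6.5 by one grade on recovery. This is not true of all of Table 12: the muscle-weakness row requires Grade 1 or lower, the confusion row requires symptoms to resolve, and pancreatitis leads to discontinuation.

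5. **Precedence.** Section 6.5 does not say that it overrides Appendix I. Tables 10 to 12 do not mention DLTs. Section 6.4 makes no carve-out.

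6. **Size of the venetoclax gap, for illustration.** The next level down in Table 9 is 600 mg from 800 mg, (800 − 600)/800 = 25%. From the Cohort 1 dose of 400 mg it is 200 mg, (400 − 200)/400 = 50%. Section 6.5 does not prescribe these steps; it leaves the reduced level to the sponsor after discussion with the investigator.

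7. **Effect on escalation.** Table 1 of Section 4.1 uses the number of subjects with a DLT. A subject with a DLT is evaluable whatever dosing follows, so the re-treatment dose cannot change that count.

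**The case against.** The best reply is that Section 6.5 is the specific rule for DLTs and Appendix I is general guidance. The appendix is headed as recommendations. Table 10 permits an unchanged dose and says only that modification is not required, and the Grade 2 restart in Table 11 is discretionary. A site that follows Section 6.5 would breach neither of those texts. Section 6.5 also has the sponsor define the reduced level after discussion, and says that continued-dosing decisions are driven by the DLT definition.

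Part of this stands: the overlap can be worked around for venetoclax, and sponsor involvement makes divergent handling less likely in a part with 6 to 12 subjects. It does not supply a rule. A site that follows Table 10 alone departs from Section 6.5, and Section 6.4 sends it to Table 10 without warning. The discussion clause concerns a reduced level, whereas Table 10 says that none is needed. Table 12 is worded less permissively than the other two tables. That the specific text beats the general one is an inference the protocol never states.

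A reader might also infer that Section 4.1 conflicts, because it says "all other AEs should resolve to" Grade 2 or lower before the next combination cycle. That is a stated minimum, and a stricter condition after a DLT can sit on top of it.

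**Conclusion.** The protocol is wrong as written, on a narrow front. For febrile Grade 3/4 neutropenia and non-excepted Grade 3/4 non-hematologic events, Section 6.5 and Table 10 differ on the venetoclax dose after a first episode. Section 6.5 and certain rows of Tables 11 and 12 differ on recovery: by one grade in the rows for other toxicities, and by up to two in the pomalidomide neutropenia row. Nothing states which text prevails. The conclusion assumes that a Cycle 1 DLT is a first episode and that the event is attributed to the drug whose table is consulted.

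Four stronger readings are tempting and not supported:

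- **All three tables conflict with Section 6.5 on dose and recovery.** Table 10 differs on dose; the rows at issue in Tables 11 and 12 reduce the dose and differ only on recovery.
- **Most DLTs, or every Grade 3/4 non-hematologic DLT, are affected.** The documents give no DLT frequencies, and the infection and clinical tumor lysis rows fall outside the dose conflict.
- **Escalation by the Bayesian optimal interval rule is distorted.** The DLT is counted regardless of re-treatment. Any influence runs through the qualitative review of later-cycle toxicity in Sections 6.1 and 6.5.
- **Section 6.5 means 600 mg after a DLT at 800 mg.** It names no level.

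**What to change.** Reconcile Section 6.5 with Tables 10, 11 and 12. State in Section 6.5, and at the head of the tables, which text governs re-treatment after a DLT, for each drug and separately for dose and for recovery level. Cover the Table 11 neutropenia row explicitly, because its criterion is an ANC value and not a grade. Add a cross-reference in Section 6.4 so that a site directed to Appendix I learns whether DLTs are handled there. Leave the Section 4.1 cycle-start minimums as they are.

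Which dose and recovery level should apply is for the sponsor and its medical team; this review takes no position. The cost is wording in a protocol amendment, with no added subjects, visits or procedures.
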